12.2 Secondary Analyses

12.2.1 Key Secondary Analyses

The key secondary efficacy variables include ocular itching at $3(\pm 1)$, $5(\pm 1)$, and $7(\pm 1)$ minutes post-CAC at visits 5 (Day 7), 6a (Day 8), 7 (Day 14), 8a (Day 15), and 8b (Day 15; 8 hours from Visit 8a).

Ocular itching scores for these time points and visits will be analyzed in a manner similar to the primary analyses using the same analysis populations and imputation methodologies for missing data. All ocular itching scores (including both key secondary and other secondary timepoints) will be included in the listing for primary efficacy ocular itching scores.

12.2.2 Other Secondary Analyses

Other secondary efficacy variables include ocular itching at $10(\pm 1)$ minutes post-CAC at visits 5 (Day 7), 6a (Day 8), 7 (Day 14), 8a (Day 15), and 8b (Day 15; 8 hours from Visit 8a), and conjunctival redness, episcleral and ciliary redness, chemosis, eyelid swelling, tearing/watery eyes, rhinorrhea, nasal pruritus, ear or palate pruritus, and nasal congestion assessed at Visits 5 (Day 7), 6a (Day 8), 6b (Day 8; 8 hours from Visit 6a), 7 (Day 14), 8a (Day 15), and 8b (Day 15; 8 hours from Visit 8a) at 7(±1), 15(±1), and $20(\pm 3)$ minutes post-CAC. Scoring scales for each assessment are presented in Appendix A.

These secondary quantitative endpoints will be analyzed in a manner similar to the primary endpoint using the ITT and PP populations with observed data only. Note that ocular itching at 10(±1) minutes post-CAC will be analyzed together with the primary efficacy ocular itching scores (including imputing missing values) even though it is considered a secondary variable.

Additionally, a composite score of the presence or absence of at least one nasal symptom will be derived for each subject based on rhinorrhea, nasal pruritus, ear or palate pruritus, and nasal congestion scores. The composite score is "Present" if at least one nasal symptom is > 0, "Absent" if all symptoms are equal to zero, and missing if any symptoms are missing and the recorded symptoms are all equal to zero.

The nasal composite scores will be summarized using counts and percentages for each response category (present, absent, missing). Nasal composite scores will be analyzed using Fisher's exact tests and Cochran-Mantel-Haenszel tests (controlling for time-appropriate Visit 4a post-CAC nasal composite scores

and including just the "Present" and "Absent" categories) at each time point for each of Visits 5 (Day 7) through 8b (Day 15).

Nasal composite scores will also be summarized as a quantitative measure calculated as the sum of the four component symptom scores (ranging from 0 to 16). If any of the four component symptom scores is missing, then the quantitative composite score will be missing. Quantitative nasal composite scores will be summarized using quantitative descriptive statistics. A two-sample test will be used to compare treatment groups at each timepoint for each of Visits 5 (Day 7) through 8b (Day 15).

All secondary efficacy endpoints will be presented in separate listings.

13. Safety Analyses

All safety analyses will be conducted using the Safety population. No inferential testing will be done for safety variables.

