#### 8.5. Visit 4a (Day -3+1 day; 24±6 hours post V3a) CAC confirmation #3

- *Update of Medical/Medication History*
- Best Corrected Visual Acuity (BCVA) using an ETDRS chart. See Appendix C.
- Pre-CAC Ocular and Nasal Allergic Signs and Symptoms Assessment
- Slit Lamp Biomicroscopy including punctum exam: A slit-lamp exam, including punctum exam, will be performed in both eyes to exclude subjects with disallowed ocular conditions. Findings of abnormality which are not exclusionary should be recorded as Medical History. See Appendix D.
- Review Inclusion and Exclusion Criteria
- Baseline Conjunctival Allergen Challenge: For each qualified subject, one drop of the allergen solution, of the same dose that elicited a positive reaction at Visit 2, will be administered bilaterally. Challenge will occur 24±6 hours following the Visit 3a challenge.
- Post-CAC Ocular and Nasal Allergic Signs and Symptoms Assessment: Assessment of itching will be made by the subject at  $3(\pm 1)$ ,  $5(\pm 1)$ ,  $7(\pm 1)$ , and  $10(\pm 1)$  minutes following allergen challenge. Assessments of redness and chemosis will be graded by the investigator and assessments of eyelid swelling, tearing/watery eyes, and nasal symptoms will be made by the subject at  $7(\pm 1)$ ,  $15(\pm 1)$ , and  $20(\pm 3)$  minutes post-challenge (see Appendix I, Appendix J and Appendix K).
- If the subject fails to react positively (i.e., an average of  $\geq 3$  itching and  $\geq 2.5$  conjunctival redness) in both eyes after the first three post-CAC assessment time points, he/she will be excluded from the study.
- Review Inclusion and Exclusion Criteria

CLN-Protocol-0052 Page **30** of **61** 

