### 10.8. Primary Efficacy Analyses

The primary efficacy endpoint is ocular itching assessed at  $3(\pm 1)$ ,  $5(\pm 1)$ ,  $7(\pm 1)$  minutes post- CAC® (0-4 scale, allowing half unit increments) at Visit 6b (Day 8; 7 days post-insertion; 8 hours from Visit 6a). The average of each subject's eyes at each post-CAC® time point will be used as the unit of analysis for ocular itching. Ocular itching will be analyzed using an ANCOVA model for each post-CAC® time point at Visit 6b, with the time appropriate post- CAC® scores at Visit 4a as a covariate and treatment group as the sole factor (OTX-DP compared to PV). Two-sample t-tests will be used as unadjusted sensitivity analyses at each

post-CAC® time point, as well as a non-parametric Wilcoxon rank sum tests (OTX-DP compared to PV). At each post-CAC® time point, a two-sided significance level of  $\alpha = 0.05$  will be used to determine statistical significance of treatment differences.

The primary efficacy analyses will be conducted on the intent-to-treat (ITT) population using the multiple imputation MCMC method for missing data as described previously. Sensitivity or supportive analyses will be performed on the ITT population using observed data only and the LOCF, BOCF and WCO methods. The PP population will also be analyzed using observed data only as a sensitivity analysis.

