### 10.9. Secondary Efficacy Analyses

Analyses will be performed on quantitative secondary endpoints in a manner similar to the primary endpoint. Qualitative measures will be analyzed using a Fisher's exact test or Chi- Square test as appropriate (OTX-DP compared to PV). Secondary endpoints include ocular itching (except at Visit 6b at  $3(\pm 1)$ ,  $5(\pm 1)$ , and  $7(\pm 1)$  minutes post-CAC), conjunctival redness, episcleral and ciliary redness, chemosis, eyelid swelling, tearing/watery eyes, rhinorrhea, nasal pruritus, ear or palate pruritus, nasal congestion, and a composite score (analyzed as a qualitative measure determined as the presence or absence of at least one nasal symptom [present/absent], and as a quantitative measure calculated as

CLN-Protocol-0052 Page **42** of **61** 

the sum of the four component symptom scores [ranging from 0 to 16]). The secondary endpoints will be analyzed for the ITT population with observed data only and for the PP population with observed data only.

In addition, quantitative analyses will include ANCOVA models which will be run at each visit, with treatment, time point, and time appropriate baseline as covariates for adjustment (accounting for repeated measurements). Least Square Means (LS Means) for each treatment, the corresponding 95% confidence intervals (CIs), and the estimated treatment difference between OTX-DP and PV will be calculated from these ANCOVA models.

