8.3 Definition of Baseline

For all efficacy variables , baseline will refer to the time specific measure at Visit 4a (e.g., ocular itching at 3 minutes post-CAC at Visit 4a will be the baseline for ocular itching at 3 minutes post-CAC at Visits 6b, 6a, 5, 8b, 8a, and 7).

For all safety variables, baseline is defined as the last measurement prior to the first dose of study medication.

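### The SAP compares the 0–16 nasal composite with an unadjusted two-sample test where the protocol calls for baseline-adjusted ANCOVA, and SAP Section 15 declares no changes

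*SAP*

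**What the plan says.** **Protocol.** Section 10.9 opens with a general rule: "Analyses will be performed on quantitative secondary endpoints in a manner similar to the primary endpoint". The endpoints it then lists include the nasal composite, both as present/absent and as a sum from 0 to 16. The primary method, in Section 10.8, is an ANCOVA at each time point with the time-matched "scores at Visit 4a as a covariate and treatment group as the sole factor". Two-sample t-tests and Wilcoxon tests appear there only as unadjusted sensitivity analyses. Section 10.9 adds a second model: "quantitative analyses will include ANCOVA models which will be run at each visit, with treatment, time point, and time appropriate baseline as covariates", allowing for repeated measurements.

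**SAP.** Section 12.2.2 lists the other secondary variables, ending at nasal congestion, and says of them: "These secondary quantitative endpoints will be analyzed in a manner similar to the primary endpoint". The composite is not in that list. It is introduced afterwards in two forms:

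- The present/absent form gets Fisher's exact tests and "Cochran-Mantel-Haenszel tests (controlling for time-appropriate Visit 4a post-CAC nasal composite scores".
- The 0–16 sum gets descriptive statistics and then: "A two-sample test will be used to compare treatment groups at each timepoint".

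SAP Section 1 states that the SAP's methods take precedence over the protocol's. SAP Section 15 states that nothing was changed from the protocol.

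**The concern.** For the summed composite, both protocol ANCOVA models have gone, and a type of test that the protocol keeps for sensitivity has become the only inferential analysis. Because the SAP governs, that test is what would be run. A reader relying on Section 15 would expect the ANCOVA.

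The result is also uneven within the SAP. The same four symptoms are adjusted for Visit 4a when analysed singly and in one of the two tests of the dichotomy, but not when added up. The covariate is available: SAP Section 8.3 says that for all efficacy variables "baseline will refer to the time specific measure at Visit 4a", and at Visit 4a (protocol Section 8.5) "assessments of eyelid swelling, tearing/watery eyes, and nasal symptoms will be made by the subject" at the same 7, 15 and 20 minutes used after treatment.

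At stake are precision, if the Visit 4a score predicts the later score; chance baseline imbalance left in the estimate; and an accurate record of departures.

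A smaller, separate matter also bears on Section 15. The protocol is inconsistent on missing data for the key secondary itching endpoints. The synopsis supports imputation: it applies multiple imputation to efficacy analyses generally and confines observed-data-only analysis to the remaining secondaries. Sections 10.7 and 10.9 point the other way: the first names only the primary variable for imputation, and the second gives secondary endpoints observed data only. SAP Section 12.2.1 imputes, and Section 15 does not mention the choice.

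**Working it through.** **The plan's own figures.** The only power figures are for itching at Visit 6b (SAP Section 5): 40 per arm, SD 1.0, two-sided 0.05, differences of 0.87, 1.08 and 1.13. From the noncentral t with 78 df and noncentrality difference × √(40/2), power is 97.0%, 99.8% and 99.9%. The product is 96.7%. All match. They do not concern the composite, for which the documents give no SD, effect or correlation; only the 40 per arm is carried forward.

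**Precision.** Let r be the correlation between the Visit 4a composite and the post-treatment composite, assumed between 0 and 0.7. With n = 40 per arm, the expected variance of the ANCOVA estimate relative to the unadjusted one, including the cost of estimating one slope, is

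(1 − r²) × (1 + 1/(2n − 4)) = (1 − r²) × 77/76 = (1 − r²) × 1.0132.

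The unadjusted SE relative to ANCOVA is one over the square root of this. For r = 0.5: 0.75 × 1.0132 = 0.760, and 1/√0.760 = 1.147. Break-even is where r² = 1/77, so r = 0.114.

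**Power.** Take the effect that the unadjusted t-test detects with 80% power at 40 per arm, about 0.634 SD. ANCOVA power uses the noncentral t with 77 df and the reduced variance.

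| r | Unadjusted SE vs ANCOVA | ANCOVA power (t-test 80%) |
|---|---|---|
| 0 | −0.7% | 79.5% |
| 0.1 | −0.2% | 79.9% |
| 0.3 | +4.1% | 83.1% |
| 0.5 | +14.7% | 89.5% |
| 0.7 | +39.1% | 97.4% |

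A simulation on bounded scores (8,000 trials per setting; four integer 0–4 scores summed; about 18% zeros, all assumed) gave SE differences of −0.4%, 0.0%, +4.6%, +16.1% and +40.4% at r = 0, 0.11, 0.30, 0.50 and 0.70, so the formula does not depend much on normality.

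**Chance imbalance.** The difference between arms in mean baseline has SD √(2/40) = 0.224 in baseline SD units, so the chance that it exceeds 0.25 SD in either direction is 26%. The unadjusted estimate shifts by r × imbalance.

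| Baseline imbalance | r = 0.3 | r = 0.5 | r = 0.7 |
|---|---|---|---|
| 0.25 SD | 0.075 SD | 0.125 SD | 0.175 SD |
| 0.44 SD (about two SDs of the imbalance; about a 5% event) | 0.13 SD | 0.22 SD | 0.31 SD |

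**Extent.** Six visits (5, 6a, 6b, 7, 8a, 8b) × three times (7, 15, 20 minutes) = 18 comparisons in each of Tables 14.2.12.3 (ITT) and 14.2.12.4 (PP).

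**The case against.** The strongest reply is that little depends on this. The unadjusted test is valid, the composite is outside the six-step hierarchy, and the SAP's precedence clause leaves no doubt which analysis will run. All of this stands and limits the seriousness. It does not make Section 15 correct.

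It can also be said that a primary-type analysis already includes two-sample tests, and that the protocol synopsis, like the SAP list, names symptoms only as far as nasal congestion. But Section 10.8 gives those tests a sensitivity role, the synopsis list is introduced as non-exhaustive, and Section 10.9 names the 0–16 sum outright. A deliberate simplification would belong in Section 15 with a reason.

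Two further points stand and add to the work. The SAP does not say whether the test is a t-test or a Wilcoxon test, although Section 12.1 uses both. And the Cochran-Mantel-Haenszel test for the dichotomy is itself an undeclared addition: protocol Section 10.9 specifies only Fisher's exact or chi-square.

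Every size above depends on an assumed r, and the gain vanishes below about 0.11. That is true, and the table shows it.

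On missing data, the SAP follows one of two available protocol readings and also reports itching with observed data only (Tables 14.2.1.6 and 14.2.1.7). Alone this would be a documentation note, and it is treated here as no more than that.

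**Conclusion.** The concern holds. The protocol requires baseline-adjusted ANCOVA for the 0–16 nasal composite, the SAP replaces it with an unadjusted and unnamed two-sample test, and SAP Section 15 is wrong to report no change. The primary result, the key secondary itching results and type I error control in the hierarchy are unaffected.

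The size depends on r. Adjustment costs at most 0.7% in standard error if Visit 4a predicts nothing. Omitting it inflates the standard error by 4.1% to 39.1% for r from 0.3 to 0.7. These figures assume 40 per arm, a linear baseline relation and equal SDs in the arms. The discrepancy between the documents rests on no assumption. It should be corrected before unmasking.

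**What to change.** - In SAP Section 12.2.2, analyse the quantitative nasal composite by the ANCOVA used for the other quantitative secondaries (time-matched Visit 4a composite as covariate, treatment as factor), and add the per-visit repeated-measures ANCOVA of protocol Section 10.9.
- Name the two-sample test (t, Wilcoxon or both) and keep it as the unadjusted sensitivity analysis.
- In SAP Section 15, list and justify any departure that remains, including the added Cochran-Mantel-Haenszel test.
- Add one sentence there saying that the protocol is inconsistent on missing data for the key secondaries and that the SAP applies MCMC imputation to them.

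The cost is SAP wording and the matching table shells. The Visit 4a nasal scores are already collected, and the model is already specified for the component scores.

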13.1 Adverse Events

An AE is any untoward medical occurrence in a patient or clinical investigation subject administered a pharmaceutical product and that does not necessarily have a causal relationship with the treatment. An AE can therefore be any unfavorable and unintended sign (including an abnormal laboratory finding), symptom, or disease temporally associated with the use of an IP, whether or not related to the IP. Treatment-emergent adverse events (TEAE) are defined as AEs that occur after the first use of IP. Per the protocol, only AEs that begin or worsen after insertion of the IP will be captured in the database for this study; therefore, TEAEs and AEs are equivalent in this study and will be denoted as AEs.

All AEs will be assigned a severity grade of mild, moderate, or severe based on the following definitions:

- *Mild:* Event is noticeable to the subject, but is easily tolerated and does not interfere with the subject's daily activities.
- *Moderate:* Event is bothersome, possibly requiring additional therapy, and may interfere with the subject's daily activities.
- Severe: Event is intolerable, necessitates additional therapy or alteration of therapy, and interferes with the subject's daily activities.

An AE is considered serious if, in the view of either the Investigator or Sponsor, it results in any of the following outcomes:

- Death
- A life-threatening AE
- Inpatient hospitalization or prolongation of existing hospitalization
- A persistent or significant incapacity or substantial disruption of the ability to conduct normal life functions
- A congenital anomaly/birth defect

Important medical events that may not result in death, be life-threatening, or require hospitalization may be considered serious when, based upon appropriate medical judgment, they may jeopardize the subject and may require medical or surgical intervention to prevent one of the outcomes listed above.

Documentation of AEs will include onset date, resolution date, location (OD, OS, both eyes [OU], nonocular), severity, action(s) taken, IP relationship, outcome, seriousness, reason for seriousness, expectedness, action taken with IP, and a description/narrative of the AE. All AEs will be coded using MedDRA classifications with reference to SOCs and PTs (MedDRA, version 20.0).

An overall summary table of AEs will be presented to report the number of AEs and the numbers and percentage of subjects who experienced at least one AE in the following categories:

- AEs
- Ocular AEs
- Non-Ocular AEs
- SAEs
- AEs by Severity
- AEs Leading to Subject Withdrawal
- AEs Resulting in Death

Additional AE summary tables will be presented by treatment and for all subjects showing the number of AEs and the number and percentage of subjects who experienced at least one AE. These summaries will be presented at the subject level by SOC and PT. If a subject reports multiple AEs coded the same SOC and/or PT, that SOC and/or PT will only be reported once. For AE summaries by severity or relationship to IP, if a subject reports multiple AEs coded to the same PT within a given SOC, the subject will be counted once under the maximum (worst) severity or relationship to IP as applicable. In the summaries, SOC will be listed in order of descending frequency for all subjects; PTs will be listed in order of descending frequency for all subjects; and non-ocular AEs separately and include the following:

- All AEs
- All AEs suspected to be related to the IP
- All SAEs suspected to be related to the IP
- All AEs by Relationship to IP
- All AEs by Severity

Subject listings will be provided for all AEs, SAEs, AEs leading to death, and AEs leading to study treatment discontinuation.

13.2 Best Corrected Visual Acuity

The logarithm of the minimum angle of resolution (logMAR) visual acuity will be assessed at each visit except for Visit 4b (Day 1) using an ETDRS chart set at 4 meters from the subject. Any subject unable to read at least 20 or more letters on the ETDRS chart at 4 meters will be tested at 1 meter. The assessment is performed pre-CAC for visits when the CAC is administered.

The observed visual acuity (at 4 meters) and change from baseline will be summarized for each eye using continuous descriptive statistics by visit and treatment group for the Safety population. The number and percentage of subjects in each treatment group with a decrease of 10 or more letters (0.2 logMAR) from baseline will also be summarized.

A subject listing of visual acuity (including any 1-meter assessments) will also be produced.

13.3 Slit-Lamp Biomicroscopy and Punctum Examination

A slit-lamp biomicroscopy and punctum examination of the eyelid, punctal appearance, lid apposition, conjunctiva, sclera, anterior chamber, cornea, iris/pupil, and lens will be performed on each eye at each visit except for Visit 1 (Day -45) and Visit 4b (Day 1). The assessment is performed pre-CAC for visits when the CAC is administered. The results will be graded as normal, abnormal not clinically significant (NCS), or abnormal clinically significant (CS). The results will be summarized for the Safety population using counts and percentages for each treatment group at each visit for each eye. Percentages will be based on the number of subjects in each treatment group with responses.

A subject listing of the slit-lamp biomicroscopy parameters will also be produced.

13.4 Intraocular Pressure (IOP)

Intraocular pressure will be assessed post-CAC by contact tonometry in each eye at Visits 2 (Day -5), 6b (Day 8), 8b (Day 15; 8 hours post Visit 8a), 9 (Day 30). The assessment is performed post-CAC for visits when the CAC is administered. Results will be taken from a single measurement and will be recorded in mmHg.

The observed IOP and change from baseline will be summarized using continuous descriptive statistics by visit, treatment group, and eye for the Safety population. The number of instances where IOP \geq 30 mmHg and increases 10 mmHg over baseline will also be summarized using counts and percentages.

A subject listing of IOP will also be produced.

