8.1 Unit of Analysis

The subject will be considered the unit of analysis for all efficacy variables (e.g., itching, redness). In cases where data are collected for each eye, the average of both eyes of each subject will be used for statistical summaries and analyses. Medical history, concomitant medications, and AEs will also be collected and presented at the subject level.

The eye will be considered the unit analysis for all safety variables (e.g., BCVA, IOP).

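### SAP 13.4 counts undefined instances of raised IOP, with no stated denominator or pooling rule, so the IOP summary may not show how many subjects per arm were affected

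*SAP*

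**What the plan says.** SAP 8.1 sets the general rule: "The eye will be considered the unit analysis for all safety variables (e.g., BCVA, IOP" are the named examples.

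SAP 13.4 schedules IOP "in each eye at Visits 2 (Day -5), 6b (Day 8), 8b (Day 15; 8 hours post Visit 8a), 9 (Day 30" being the exit visit. It adds: "Results will be taken from a single measurement and will be recorded in mmHg". The continuous values and changes are "summarized using continuous descriptive statistics by visit, treatment group, and eye for the Safety population". The threshold sentence comes next: "The number of instances where IOP" is at least 30 "mmHg and increases 10 mmHg over baseline will also be summarized using counts and percentages". No denominator follows, and nothing says how eyes and visits are combined. A subject listing of IOP is planned.

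Other safety sections count subjects. SAP 13.2 gives "The number and percentage of subjects in each treatment group with a decrease of 10 or more letters (0.2 logMAR) from baseline". SAP 13.5 counts subjects whose fundoscopy worsens. SAP 13.3 and 13.5 also state that their percentages are taken over subjects with responses in each arm; 13.4 has no such sentence. Protocol 10.11 says only that IOP is summarised descriptively, so it does not settle the unit.

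**The concern.** IOP elevation is a listed risk of the insert (Protocol 4.5.2) and one of the main local concerns with ocular steroids (Protocol 4.2). The clinical reader wants to know how many subjects in each arm had a marked elevation. An instance count does not answer this. A subject with persistent elevation in both eyes can be counted several times, and the same total can come from several subjects. Because the percentage has no denominator, the programmer must choose one. With about 40 subjects per arm, events may be few, and the choice of unit could then drive the printed figure. The point concerns the unit and denominator, not the mmHg cut-off.

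**Working it through.** The plan states no IOP count or rate, so there is no figure to reproduce. The check enumerates what the table could show.

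**Inputs.** 40 subjects per arm (SAP 5); same treatment in both eyes (SAP 4.1); three scheduled post-insertion IOP visits, 6b, 8b and 9, with one reading per eye (SAP 13.4). Complete data are assumed.

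**Readings.** Per subject: 2 eyes × 3 visits × 1 reading = 6. Per arm: 40 subjects, 40 × 2 = 80 eyes, 40 × 6 = 240 eye-visits.

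**Two cases.** Case A: one subject raised in both eyes at Visits 8b and 9. Case B: four different subjects each raised once, one in each of right eye 8b, left eye 8b, right eye 9 and left eye 9.

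| Tabulation | Case A | Case B |
|---|---|---|
| Instances, pooled over eyes and visits | 4 | 4 |
| Instances by visit, eyes pooled | 2 at 8b, 2 at 9 | 2 at 8b, 2 at 9 |
| Instances by visit and eye | 1 in each of four cells | 1 in each of four cells |
| Subjects, either eye, by visit | 1/40 = 2.5% at 8b and at 9 | 2/40 = 5.0% at 8b and at 9 |
| Subjects, either eye, any visit | 1/40 = 2.5% | 4/40 = 10.0% |

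All three instance layouts are identical for the two cases. The any-visit subject rate differs by 10.0/2.5 = 4-fold.

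**How many subjects four instances can represent.**
- Pooled over eyes and visits: at least 4/6 rounded up = 1, at most 4.
- Within one visit, eyes pooled: at least 4/2 = 2, at most 4.
- Within one visit-and-eye cell: exactly 4, because a subject enters a cell once.

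A single visit-and-eye cell is therefore a true subject count. The loss arises when cells are combined, because the table does not show which cells share a subject.

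**Percentages for four instances, by denominator.**

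| Denominator | Printed | Against Case A (2.5%) | Against Case B (10.0%) |
|---|---|---|---|
| 40 subjects | 4/40 = 10.0% | 4-fold too high | correct |
| 80 eyes | 4/80 = 5.0% | 2-fold too high | 2-fold too low |
| 240 eye-visits | 4/240 = 1.7% | 1.5-fold too low | 6-fold too low |

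The distortion can go in either direction.

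**The case against.** The strongest reply is that the SAP never asks for a pooled count. SAP 8.4 presents summaries by treatment group and, where appropriate, by visit unless stated otherwise. The sentence before the threshold count in 13.4 splits by visit and eye, and 8.1 makes the eye the unit. The natural layout is then a by-visit, by-eye count, in which each cell counts subjects. This stands, and it rules out three stronger readings that a reader might infer:

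- That the percentage will be taken over 240 readings and will understate the subject rate 6-fold. The SAP does not name that denominator, and with 40 as denominator the error can be an overstatement.
- That any bilateral case looks like four subjects. At one visit a bilateral case gives 2 instances, so the confusion is one subject against two. It takes both eyes at two visits to reach four.
- That 8.1, 13.2 and 13.4 contradict one another. Counting subjects within each eye fits an eye-level unit, and 13.3 and 13.5 work this way. Only the instance wording in 13.4 stands apart.

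The reply also notes that the IOP listing identifies subjects, that ocular AE tables count each subject once per preferred term (SAP 13.1), and that no inferential safety testing is planned (SAP 13). All true. But a listing is not a summary by arm, and an AE table covers only elevations reported as AEs. The by-visit, by-eye layout also does not remove the problem, since Cases A and B give the same table under it.

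**Conclusion.** The point holds as a minor improvement. SAP 13.4 leaves the instance, its denominator and the pooling over eyes and visits undefined, and none of the plausible layouts guarantees the number of affected subjects per arm. The size is illustrative: the same table can stand for 2.5% or 10% of an arm, and four instances can be printed as 10.0%, 5.0% or 1.7%. These figures assume 40 treated subjects per arm with complete scheduled IOP data, and they rest on constructed cases. If all four readings fell in one visit-and-eye cell, a by-visit, by-eye table would show four subjects correctly. The documents do not support saying that affected subjects cannot be identified, because the listing allows it. Only a descriptive safety table is affected; efficacy conclusions, Type I error and power are not.

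**What to change.** In SAP 13.4, replace the instance count with the number and percentage of subjects who have at least one eye meeting the stated criterion, by visit and at any post-insertion assessment. For the any-visit figure, use as denominator the Safety subjects with a baseline and at least one post-insertion IOP. Keep a by-visit, by-eye count alongside. State whether unscheduled readings enter the any-visit count; SAP 8.4 excludes them only from by-visit summaries. In the same edit, say whether the two IOP conditions are joint or counted separately, since the sentence can be read both ways.

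Apply the same either-eye, any-visit subject rule to the 10-letter loss in 13.2, and limit the eye as unit in 8.1 to eye-level descriptive summaries.

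The cost is SAP wording and a few rows in Tables 14.3.2 and 14.3.4, from data already planned for collection. Settle it before unmasking, so that the unit is not chosen with results in view.
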